15.8 Interim Analysis

Once accrual to Groups I and II are complete, analyses will be conducted to help determine whether accrual of patients to Groups I and II should continue in order to assess the impact of Td toxoid pre-conditioning within subgroups defined by CMV status. Based upon these analyses and other factors, one of 3 decisions will be made: 1) Continue accrual to both CMV positive and CMV negative strata within Groups I and II; 2) Continue accrual to only one CMV stratum within Groups I and II; or 3) Terminate accrual to all arms. It should be noted that there are no options to continue accrual to Group III once the initial sample size goals are attained.

At the time that this interim analysis is conducted, the number of deaths required per Section 15.9.2 for the overall comparison of survival within Groups I and II to have the desired power will not have yet been attained. With the assumptions described in Section 15.9.2, we anticipate that a total of 31 deaths will have occurred in Groups I and II combined by the time of these interim analyses if the alternative hypothesis is true.

Based upon data available at the time of the interim analysis, the conditional probability of observing a statistically significant result within each CMV subgroup will be generated. That calculation will account for the accrual rate observed to date within each subgroup, which reflects both overall accrual and the prevalence of CMV positivity. The sample size requirements provided in Sections 15.9.4 and 15.9.5 will also be adjusted to reflect subgroup accrual rates observed to date.

Factors that will be considered in the decision to extend accrual to address subgroup efficacy questions include the conditional probability referenced above, as well as the feasibility of completing extended subgroup accrual in light of accrual rate and competing priorities.

15.9 Sample Size Calculation

The following sections concerning sample size and power reflect the study as it was originally designed. Per Section 9.1, the randomization of patients to Group III has been terminated with AMD 49. Otherwise, the overall design of the rest of the study remains.

Our goal remains to randomize a total of 35 patients to Groups I and II each. As described in Section 15.9.2, a 1-tailed logrank test will be conducted at the 0.15 level of significance to compare survival in Group I and II. For this comparison to have 90% power to detect a hazard ratio of 0.5, 45 deaths need to be observed within the two arms being compared.

At this time, approximately 35 patients have been randomized to each of Groups I and II, the interim analysis described in section 15.8 will be conducted to determine whether accrual of patients to CMV subgroups should continue.

Included in the following sample size and power calculations are estimates of the time required to complete accrual and observe the required number of events. Though these estimates are no longer valid, re-estimates will not be generated due to the rate of randomizing patients to Groups I and II having varied over time due to the number of randomizing arms as well as early problems with vaccine contamination.

15.9.1 Overview of Sample Size Requirements

A maximum of 100 patients will be initially enrolled in this study over a period of 29 months with the expectation that approximately 79 patients will be randomized after completion of radiation with concurrent temozolomide. Justification for the required number of randomized patients for the key primary outcome variables are provided below. The sample size calculations described in Section 15.9.2 for the key primary objective and the primary subgroups objectives reflect the fact that accrual to Group III was initiated a few months after accrual was initiated on Groups I and II.

At the time that accrual to Groups I and II are completed, a decision will be made concerning the accrual of additional patients to address efficacy questions within CMV subgroups (see Section 15.8). A priori sample size requirements for subgroups are described in Sections 15.9.4 and 15.9.5; however, these calculations will be updated at the time of the interim analysis to reflect observed subgroup accrual rates. At the time of writing this protocol, we anticipate that a maximum of 64 additional patients will be accrued during the extended accrual period so that 58 additional patients will be randomized to Groups I or II.

Hence, a maximum total of 180 patients will be accrued to this study so approximately 160 patients will be randomized.

Sample size requirements for the migration studies are provided in Section 15.9.3. As described in that section, the first 12 patients in Groups I and II will undergo migration studies are be used in those analyses.

15.9.2 Key Primary Objective: Survival

The key primary goal of this study is to determine whether the addition of either Td pre-conditioning with vaccination #4 or basiliximab administration with vaccination #1 and #2 that is administered in conjunction with DC vaccination and temozolomide is worthy of investigation in a large phase III study. Two pairwise comparisons of survival are of primary interest: 1) Td Toxoid arm (Group II) versus Unpulsed DC arm (Group I), and; 2) Basiliximab arm (Group III) versus Unpulsed DC arm (Group I).

Though this phase II study is comparative, a false-positive rate of 0.15 will be used to test each hypothesis while maintaining reasonably high power[128-130]. This rate of false-positivity is used in lieu of a false positive rate of 0.2 as suggested in the literature in an attempt to partially adjust for there being multiple comparisons.

Within the ATTAC study, the median survival in the DC vaccine arm without pulsed DC pre-conditioning was approximately 12 months; whereas, within the Td pre-conditioning arm median survival was estimated to be approximately 36 months. Study results suggest a hazard ratio of approximately 0.33. Due to the small sample sizes in the ATTAC study, estimates are all associated with wide confidence intervals. Given these imprecise estimates and the potential for “regression to the mean” in this study replicating the ATTAC trial, we will target a smaller hazard ratio of 0.5 for a comparison of unpulsed DC (Group I) and Td (Group II). With pilot data not being available for the comparison of basiliximab (Group III) and unpulsed DC (Group I), we will also target a hazard ratio of 0.5 for that comparison.

For each pairwise comparison, a 1-tailed logrank test will be conducted at the 0.15 level of significance. In order that each comparison will have 90% power to detect a hazard ratio of 0.5, 45 deaths need to be observed within the two arms being compared[131].

We anticipate that patients will be accrued at the rate of 4 patients per month, with a randomization rate of 3.5 patients per month. As described earlier, the protocol was initially activated with only Groups I and II. However, with a later amendment, patients will be randomized to one of 3 arms. In the following calculations, we will assume that there is a period of 2 months during which patients are randomized to one of 2 arms after which patients will be randomized to one of 3 arms. Tabulated below is the anticipated accrual and randomization rate within each arm during each period of accrual.

Table 5. Anticipated Accrual and Randomization Rates

# of Arms Accruing	Accrual Rate (Patients / Month / Arm)	Randomization Rate (Patients / Month / Arm)
2 arms	2	1.75
3 arms	1.33	1.17

Approximately 32 patients will be randomized to Group III before accrual will be terminated to Group III and the interim analysis described in section 15.8 conducted. Per Section 9.1, the randomization of patients to Group III has been terminated with AMD 49. At the time approximately 35 patients have been randomized to each of Groups I and II, the interim analysis described in section 15.8 will be conducted to determine whether accrual of patients to CMV subgroups should continue. At the time of this interim analysis, we anticipate that approximately 35 patients will have been accrued to Groups I and II each and that a total of 31 patients within Groups I and II will be dead under the alternative hypothesis where the median survival in Group I is 12 months and the median survival in Group II is 24 months. Approximately 12 months are needed after the last patient randomization to observe 45 events[132-134].

In addition to the comparison of Groups I and II, we plan to compare the survival of patients enrolled on Arms I and III. Under the null hypothesis, approximately 13 month of follow-up after the last patient randomization is required to observe 45 events.

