All enrolled patients will undergo a leukapheresis after resection for harvest of PBLs for generation of DCs. Patients will then receive approximately 6 weeks of standard of care RT and concurrent TMZ at a standard targeted dose of 75 mg/m²/d (please see Package Insert uploaded in eIRB for standard therapy). Patients should start RT within approximately 6 weeks of surgery. Patients who either experience progressive disease during radiation, are dependent on steroid supplements above physiologic levels at time of first vaccination, are unable to tolerate TMZ, or whose DCs or PBLs fail to meet release criteria will be withdrawn from the study and replaced and will not undergo repeat leukapheresis. For patients whose initial leukapheresis yields less than 3 vaccines, repeat leukapheresis may be obtained a minimum of 2 weeks from the previous leukapheresis (and may be repeated as needed) if pre-pheresis blood work is within the Apheresis Center's parameters and as long as this does not cause a significant delay in treatment for the patient. At the post-RT clinic visit where patient's MRI and blood work is evaluated prior to ordering the first post-RT cycle of TMZ, patients will be randomized to receive DC vaccination with one of three treating regimens: Group I: unpulsed DC pre-conditioning prior to vaccination #4; Group II: Td pre-conditioning prior to vaccination #4; or Group III: basiliximab infusions at vaccination #1 and #2 with Td pre-conditioning prior to vaccination #4. As of March 2017 (AMD 49), randomization of patients to Group III has been terminated. Please see Section 9.1.1 for a detailed outline of the randomization strategy for vaccine site pre-conditioning and Section 9.1.7 for a detailed description of the double blinding process. The study cycle of TMZ comprises a targeted dose of 150-200mg/m²/d for 5 days every 5 (± 1) weeks. All patients will receive up to a total of 10 DC vaccines given bilaterally at the groin site unless progression occurs. DC vaccines will be given i.d. and divided equally to both inguinal regions. DC vaccines #1-3 will be given every two weeks, thus delaying the initiation of TMZ cycle 2 for all patients. All remaining TMZ cycles will continue every 5 (± 1) weeks. Before the first DC vaccination, patients will receive 0.5 mL of Td (tetanus and diphtheria toxoids adsorbed) intramuscularly into the deltoid muscle to ensure adequate immunity to the tetanus antigen. The Td vaccine will be obtained through Duke Investigational Chemotherapy Services (ICS) Pharmacy. All patients will undergo leukapheresis again for immunologic monitoring with specific assessment of baseline antigen-specific cellular and humoral immune responses and further DC generations 4 ± 2 weeks after vaccine #3.

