9.1.7 Study Drug(s) Blinding

The Duke ICS Pharmacy will be responsible for the preparation of the Td and the saline used for the pre-conditioning done prior to the fourth vaccine. The unpulsed DCs used for pre-conditioning will be prepared in the DBTIP Laboratory and delivered to the ICS for the labeling and distribution of the blinded pre-conditioning drugs (i.e., Td, unpulsed DCs, and saline). Only those key personnel needed for the preparation and distribution of the pre-conditioning drugs will be unblinded (i.e., ICS pharmacy staff and DBTIP Lab study drug manufacturing personnel, as well as the statisticians). The patient and the remaining key personnel (including the PI and research nurses administering the pre-conditioning drugs) will be blinded to the pre-conditioning regimen. Emergency unblinding procedures are described in [13.3](#).

The administration of pre-conditioning agent (Td or unpulsed DCs) will be blinded for Groups I and II, however, the administration of the pre-conditioning agent (Td) and basiliximab for Group III will not be. Hence, patients and providers will know when a patient has been assigned to the third treatment group (please see randomization and blinding SOP [18.2](#) in appendices).

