⁷ Initial leukapheresis will be scheduled following consent. Per standard Duke Apheresis Protocol, all subjects will have CBC, CMP, ionized Calcium, and βHCG within 48 hours prior to the procedure(s). Follow up leukapheresis will occur approximately 4 ± 2 weeks after third immunization to obtain PBMCs for Immunologic Monitoring and generation of additional DCs for continued vaccinations. Leukapheresis can be obtained up to every 2 weeks if needed according to the Duke Apheresis Center protocol, but these will likely be needed less than every 2 months throughout the study to generate enough DCs to continue vaccinations. Blood for immune monitoring will be drawn prior to each leukapheresis (1 red top tube – approximately 4 mLs).

Appointment	Time and Range	Tumor Pathology ¹	Physical and Neurologic Exam KPS, MMSE ²	MRI ³	CMV Screen ⁴	CMP and CBC ⁵	Blood for immunologic monitoring and Sub-clinical Autoimmunity ⁶
TMZ Cycle 2 (slight delay start)	To start following V#3		X	X		X	
Pre-conditioning ⁸	1 day before V#4		X			X	X
Vaccine # 4 ⁹ (¹¹¹ In-labeled DCs) (Groups I & II only)	Day 21(± 2 days) of second cycle of TMZ						X
Migration studies ¹⁰	1 day and 2 days after V#4						X
Vaccines with Cycles of TMZ ¹¹	On day 21 (± 2 days) of each cycle of TMZ		X	X		X	X
Monthly Vaccines After TMZ not to exceed 10	Every month (± 2 weeks)		X	X		X	X
Progression ¹²		X		X			X

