12.4 Follow-up Period

Patients will be followed for survival, progression, and subsequent therapies only, and this data will be recorded by the research team. For recording of subsequent therapies, the type of therapy(ies) that the subject receives will be recorded with approximate start and stop date, if

⁸ On day before the fourth DC vaccine, patients will receive vaccine site pre-conditioning strategy (Group I-unpulsed DCs i.d.; Group II and III- Td i.d.). A single dose of Td toxoid (1 flocculation unit, Lf) or 1 x 10⁶ autologous unpulsed DCs will be administered to a single side of the groin 12-24 hours prior to the fourth DC vaccine, which is always given bilaterally at the groin site. Standard of care blood for CBC and CMP will be drawn during the pre-conditioning visit. 2 yellow and 1 red top tubes for immune monitoring will be obtained during the pre-conditioning visit.

⁹ At the day of the 4th vaccine (prior to administration), 9 yellow and 2 red top tubes obtained for immune monitoring. Patients in Groups I and II will then receive ¹¹¹In-labeled DCs to compare the effects of different skin preparations on DC migration followed by SPECT/CT imaging immediately.

¹⁰ SPECT/CT imaging will be performed at 1 and 2 days after injection of Vaccine #4 for patients in Groups I and II. At the SPECT/CT imaging visits 1 and 2 days after Vaccine #4, 2 yellow and 1 red top tubes for immune monitoring will be obtained only on patients randomized to Groups I and II (not Group III).

¹¹ Monthly cycles of TMZ will be initiated at the discretion of the treating neuro-oncologist according to pathology.

¹² As part of standard care for these patients, upon tumor progression, participants may undergo stereotactic biopsy or resection. As this is not a research procedure consent will be obtained separately. However, if tissue is obtained, it will be used to confirm tumor progression histologically and to assess immunologic cell infiltration and pp65 antigen escape at the tumor site.

possible. For subjects who complete all 10 study vaccines without progressing, an attempt will be made to obtain blood for immunologic monitoring 2-3 times a year at standard Duke Preston Robert Tisch Brain Tumor Center visits. If the subject progresses in the follow-up period, blood for immunological monitoring will be drawn at the time of progression, if possible.

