15.5.1 Key Primary Objective: Overall Survival

The Kaplan-Meier estimator will be used to describe the survival within each of the 3 treatment arms. Median survival will be estimated within each arm, with 95% confidence intervals. OS will be defined as the time between randomization and death, or last follow-up if alive. Two pairwise one-tailed log-rank tests will be conducted to assess the impact of Td and/or basiliximab. One test will compare the survival experience of patients in the TD toxoid arm (Group II) and the unpulsed DC arm (Group I), and the other test will compare the survival experience within the basiliximab arm (Group III) and the unpulsed DC arm (Group I). An intent-to-treat philosophy will be followed in these analyses.

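### The stated 90% survival power for Group II versus Group I takes a hazard ratio of 0.5 from randomization, but the arms are treated alike until about Day 69; on the plan's own survival model power is about 79% to 86%, with perhaps no loss under the stated medians if early deaths are few

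*Combined protocol and SAP*

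**What the plan says.** Section 15.9.2 sets the target for each pairwise comparison, with a one-tailed log-rank test at 0.15: "In order that each comparison will have 90% power to detect a hazard ratio of 0.5, 45 deaths need to be observed". It describes "the alternative hypothesis where the median survival in Group I is 12 months and the median survival in Group II is 24 months". Section 15.9 repeats the power for Group I versus Group II: "For this comparison to have 90% power to detect a hazard ratio of 0.5, 45 deaths need to be observed". Section 15.5.1 fixes the time origin: "OS will be defined as the time between randomization and death, or last follow-up if alive".

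The treatment schedule is as follows.

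- Section 9.1 places randomization at the post-radiotherapy visit: "prior to ordering the first post-RT cycle of TMZ, patients will be randomized to receive DC vaccination with one of three treating regimens".
- Groups I and II then receive the same Td booster, temozolomide and vaccines #1 to #3. In Table 4 (Section 12.2), vaccine #3 is on Day 49 and temozolomide cycle 2 starts after it. Vaccine #4 is on "Day 21(± 2 days) of second cycle of TMZ".
- The arms separate only at Table 4, footnote 8: "On day before the fourth DC vaccine, patients will receive vaccine site pre-conditioning strategy". Group I receives unpulsed dendritic cells and Group II receives Td.

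Section 9.4 puts all randomized patients in the survival analyses, and Section 9.1 stops vaccination at progression. Section 15 mentions neither a delayed effect nor patients who never reach vaccine #4.

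**The concern.** For roughly the first 2.3 months the hazard ratio between Groups I and II is 1 by design. Deaths in that period count toward the 45 but carry no information about Td. A calculation that applies a ratio of 0.5 from randomization credits those deaths with a treatment effect they cannot have.

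The key primary question is whether Td pre-conditioning merits a phase III trial. A negative result would be read against the stated power. If the true figure is 79%, the chance of missing a real effect of the planned size is about 21% rather than 10%, and a null result would be given more weight against Td than it deserves.

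**Working it through.** **Inputs.** One-sided 0.15 log-rank test, hazard ratio 0.5, 90% power, 45 deaths, medians of 12 and 24 months (15.9.2); 35 per arm (15.9); entry at 1.75 per arm per month for 2 months, then 1.17 for 27 months (Table 5 and 15.9.4); survival from randomization (15.5.1); visit days from Table 4.

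**1. The plan's figure.** Schoenfeld: deaths = 4(1.036 + 1.282)² / (ln 0.5)² = 44.7, so 45. Power at 45 deaths: Φ(0.693 × √45 / 2 − 1.036) = 90.1%. Simulating the design with no lag gives 89% to 90%. The stated figure is correct under proportional hazards from time zero.

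**2. The lag.** 49 + 21 − 1 = Day 69, and 69 / 30.44 = 2.27 months. This is counted from the start of cycle 1, which follows randomization, and assumes cycle 2 starts straight after vaccine #3.

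**3. Deaths before the arms differ.** With a constant 12-month-median hazard, 1 − 0.5^(2.27/12) = 0.123. Of 70 patients that is 8.6 deaths, or 8.6 / 45 = 19% of the target.

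**4. The two stated targets no longer coincide.**

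- A ratio of 0.5 after the lag gives a Group II median of 2.27 + (12 − 2.27) / 0.5 = 21.7 months.
- Keeping 24 months needs a ratio of (12 − 2.27) / (24 − 2.27) = 0.448 after the lag.

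**5. Power with the lag.** Approximation: Φ(|ln HR| × D / 4 / √(45/4) − 1.036), where D = 45 − 8.6 = 36.4 deaths after the lag.

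- HR 0.5: 0.693 × 36.4 / 4 / 3.354 = 1.88, giving 80%. Simulated: 79%.
- HR 0.448: 0.803 × 36.4 / 4 / 3.354 = 2.18, giving 87%. Simulated: 86%.

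**6. Sensitivity to early deaths.** Simulated power, with the control median held at 12 months. The ratio that keeps 24 months is 0.448 in every row, because the cumulative hazard remaining at Day 69 is the same in both arms.

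| Hazard before Day 69, relative to that assumed | Deaths before Day 69 | Power, HR 0.5 afterwards | Power, 24-month median kept |
|---|---|---|---|
| 100% | 8.6 | 79% | 86% |
| 75% | 6.5 | 82% | 89% |
| 50% | 4.4 | 84% | 90–91% |
| 25% | 2.3 | 87% | 93% |

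The comparator is 89% to 90% with no lag.

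**7. Factors that lower power further.**

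- Table 4 lists the second leukapheresis (4 ± 2 weeks after vaccine #3) before cycle 2. If cycle 2 waits for it at 4 weeks, pre-conditioning moves to about Day 97. Power is then about 74% (HR 0.5) or 84% (24 months kept), at the full early hazard.
- Non-receipt has no rate in the documents. Assuming 10% or 20% of Group II never receive Td, power at the full early hazard is about 72% or 66% (HR 0.5), and about 80% or 74% (24 months kept). These rates come on top of the 12.3% who die before Day 69, so in total 1 − 0.877 × 0.9 = 21% or 1 − 0.877 × 0.8 = 30% would not reach pre-conditioning.

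**The case against.** Four arguments on the other side have weight.

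- **The hazard ratio of 0.5 could be the average effect from randomization, lag included.** Section 15.9.2 does not use the word constant, and on this reading about 90% stands. Sections 9.2 and 15.9.3 present the trial as a replication of the pilot, so the pilot's 0.33 might already contain a lag. However, 15.9.2 attributes the move from 0.33 to 0.5 to imprecision and regression to the mean, not delay. Section 15.9.3 also describes pilot randomization as taking place before the fourth vaccination, after three vaccines. The pilot's survival origin is not given, so the point is undecided and the plan should settle it.
- **Early deaths are probably fewer than 12%.** Section 11 requires residual disease under 1 cm, good performance status and no progression on the post-radiotherapy MRI. This stands, and it is why the result must be given as a range.
- **Section 15.9.2 does state an alternative, 12 versus 24 months, and the 79% case departs from it.** This also stands. Under those medians with full receipt the loss is at most about 4 points at Day 69, and may be nil.
- **Enrollment closed in April 2018, and Section 15.1 concedes that survival may be underpowered.** That caveat concerns the early closure. The lag acts even with 35 per arm and 45 deaths, and Section 15.9 still carries the 90%.

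If the effect after pre-conditioning were as large as the pilot's 0.33, power would be about 96% despite the lag.

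**Conclusion.** The point holds as a matter of stated assumptions. The 90% needs proportional hazards from randomization, which the schedule rules out for about the first 2.3 months. With a constant 12-month-median control hazard, full receipt, 35 per arm and 45 deaths, Group II versus Group I power is about 79% (HR 0.5 after pre-conditioning) to 86% (24-month median kept). At half the early hazard it is about 84% to 90%. Non-receipt lowers all of these by an amount the documents do not allow one to fix.

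Four stronger readings are tempting and not supported.

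- **That 79% to 86% bounds the power.** It does not: with few early deaths and the stated medians there is no shortfall.
- **That the comparison is biased.** Care is the same in both arms before pre-conditioning, so this is dilution, and the intent-to-treat test keeps its size.
- **That a test of survival from the pre-conditioning date is required.** It would drop randomized patients. In an illustrative no-effect check (half the patients at 1.5 times and half at 0.5 times the hazard, with 10% of one arm, all high-risk, missing pre-conditioning), it rejected 11.9% or 19.2% of the time, depending on the arm, against a nominal 15%.
- **That the figures carry over to Group III versus Group I.** Basiliximab starts at about Day 14, so they do not.

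The number randomized at closure is not given. All figures are for the planned 35 per arm.

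**What to change.** In Sections 15.9 and 15.9.2:

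- State that Groups I and II cannot differ before pre-conditioning, nominally about 2.3 months after cycle 1 starts.
- Name the target. The natural choice is the 12- and 24-month medians already in 15.9.2, with the implied ratio of about 0.45 after pre-conditioning. If a ratio of 0.5 after pre-conditioning is meant, say so.
- Restate Group II versus Group I power at 45 deaths as about 79% to 86% under the constant 12-month-median hazard, rising to about 84% to 90% at half the early hazard, before any non-receipt.

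In Section 15.4, report the number in each arm who did not receive pre-conditioning. The split by arm matters because the two agents have different supply routes: "The unpulsed DCs used for pre-conditioning will be prepared in the DBTIP Laboratory and delivered to the ICS", whereas Td comes from the pharmacy. Section 15.4 already tabulates vaccines received by arm, so this adds little work.

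Keep the intent-to-treat log-rank test from randomization and the 45-death target. Regaining about 90% at HR 0.5 after the lag would take roughly 62 to 65 deaths among 70 patients, which is not proposed here.

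The cost is a few sentences and, in most of these scenarios, a less favourable stated power. No patients, visits or follow-up are added.
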